- Subjects who are qualified to enter A3921092 extension study and do so >14 days (but ≤3 months) after early termination or end of study (EOS) visit in qualifying study must undergo re-screening procedures and have separate visit for baseline activities. Baseline visit must occur 2-28 days after Screening visit.
- Subjects who are qualified to enter A3921092 extension study and do at the end of study (EOS) visit in qualifying study do not need to be rescreened or have an additional baseline visit.

3. Subjects who are qualified to enter A3921092 extension study and do not do so at the end of study (EOS) visit but <14 days after early termination or EOS in parent study do not need to be re-screened but require procedures performed for baseline.
4. For those subjects that complete the study, follow-up phone call will be made to subjects within 7 days after the 28 days following EOS visit and adverse events noted.
5. If a subject discontinues from the study due to abnormal hematology or clinical chemistry results which meet criteria as described in [Appendix 4](#), or discontinues due to an adverse event, a follow-up visit must be performed after the Early Termination visit within 28 days (± 7 days) of last dose of study treatment.
6. Disease Activity Assessment must be performed on subjects who enroll >14 days after end of study visit in qualifying study to determine if subject has sufficient evidence of PsA disease activity to warrant use of tofacitinib as a DMARD ([Section 7.1.1](#)).
7. Cardiovascular (CV) Risk Factor Assessment includes multiple assessments such as smoking status, average weekly alcohol consumption, and family history of premature coronary heart disease (CHD) (See [Section 7.4](#) for complete list).
8. Complete physical exam should be performed annually (Month 12, 24 and 36) and includes: height, weight, general appearance, skin, HEENT (head, eyes, ears, nose and throat), heart, lungs, abdomen, lower extremities, neurologic and lymph nodes. Targeted physical exam should be performed at other scheduled visits and includes: weight, examination of heart, lungs, abdomen, lower extremities (for peripheral edema) and lymph nodes.
9. 12-lead ECG will be taken at annual visits (Month 12, 24 and 36) and Early Termination (ET) visit only. ECG will be evaluated by a central reader.

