6. Subjects who are already taking oral corticosteroids (but not injectable) may participate in the study:
- Oral corticosteroids: Subjects who are already receiving oral corticosteroids must be on a stable dose of ≤ 10 mg/day of prednisone or equivalent for 4 weeks prior to first dose of study drug.
 - Injected (eg, intraarticular, intramuscular or intravenous) corticosteroids: Discontinued 4 weeks prior to the first dose of study drug.
7. Subjects who are already taking NSAIDs/Cyclooxygenase-2 (COX-2) inhibitors may participate in the study provided that that the dose is stable for one week prior to first dose of study drug.

4.1.2. Inclusion Criteria That Apply to Subjects Who Enroll Into This Study After the 14 Day Window From the End of Study Visit of the Qualifying Study

1. Time from End of Study visit of qualifying study must be ≤ 3 months.
2. In the opinion of the investigator, the subject must have sufficient evidence of PsA disease activity to warrant use of tofacitinib as a DMARD.
3. Subject has discontinued all disallowed concomitant medications for the required time prior to the first dose of study medication and is taking only those concomitant medications in doses and frequency allowed by the protocol (see [Appendix 3](#)). Subjects who are receiving any investigational or marketed treatment for PsA or psoriasis not mentioned elsewhere must have that treatment discontinued for 4 weeks or 5 half-lives, whichever is longer. Discontinuation criteria for biologics not otherwise mentioned must be discussed with the Pfizer Study Clinician.
4. Screening 12-lead electrocardiogram (ECG) that does not demonstrate clinically relevant abnormalities (as determined by central reader) which may affect subject safety (eg, pattern of acute myocardial infarction, acute ischemia or serious

- arrhythmia) or interpretation of study results (eg, continuously paced ventricular rhythm or complete left bundle branch block).
5. No evidence of active or latent or inadequately treated infection with *Mycobacterium tuberculosis* (TB) as defined by all of the following:

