6.1.1.2. Baseline Visit

This visit must occur 2-28 days after screening visit.

Subjects are required to fast for at least 9 hours prior to the visit, however, blood collection for laboratory testing may be taken up to 48 hour prior to the Baseline/Day 0 visit as necessary to ensure the samples are collected in a fasting state.

All Patient Reported Outcomes should be performed before any other study procedures. These include the following:

- Patient's Assessment of Arthritis Pain (VAS).
- Patient's Global Assessment of Arthritis (VAS).
- Health Assessment Questionnaire – Disability Index (HAQ-DI).
- BASDAI.
- ASQOL.
- Patient's Global Joint and Skin Assessment (PGJS-VAS).
- SF-36 Version 2 (Acute).
- DLQI.
- FACIT Fatigue Scale.
- EuroQol 5 Dimensions (EQ-5D).
- ISI.
- WLQ.
- PsA-HCRU.

Procedures that will be performed prior to enrollment and the first dose of study drug on Visit 1, Day 1 for baseline include:

- Targeted Physical Examination: (weight, examination of hearts, lungs, abdomen, lower extremities and lymph nodes).
- Vital signs: blood pressure, pulse rate and temperature (tympanic, oral or temporal preferred).

- Waist and hips circumference.
- Blood and urine specimen testing: Central laboratory tests include: Hematology, Chemistry Panel, Lymphocyte subset analysis (FACS), Hemoglobin A1c (HbA1c), C-Reactive Protein (CRP), Lipid Profile (fasting), Urinalysis.
- Urine Pregnancy Test (for women of childbearing potential only).
- Clinical Evaluation of Rheumatology Endpoints:
 - Tender/painful joint counts (68);
 - Swollen joint counts (66);
 - Physician's Global Assessment of Arthritis (VAS);
 - Assessment of presence and severity of dactylitis;
 - Assessment of enthesitis using the Spondyloarthritis Research Consortium of Canada (SPARCC) Enthesitis Index and Leeds Enthesitis Index.
- Clinical Evaluation of Dermatology Endpoints:
 - Physician's Global Assessment of Psoriasis (PGA-PsO);
 - Psoriasis Area and Severity Index (PASI);
 - Body Surface Area (BSA);
 - Nail Psoriasis Severity Index (NAPSI).
- Clinical Evaluation of Rheumatology and Dermatology Endpoint: Physician's Global Assessment of Psoriatic Arthritis (VAS).
- Drug dispensing.
- Monitoring of adverse events and concomitant treatment.

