7.6.2. Electrocardiogram

Twelve-lead electrocardiograms (ECGs) will be obtained on subjects who enroll into this study >14 days after end of study visit in qualifying study, at annual (Month 12, 24 and 36) and Early Termination visits. All ECGs should be performed after the subject has rested quietly for at least 10 minutes. ECG data will be submitted to a central laboratory for measurement. Any clinically significant changes from the baseline ECG (from qualifying study for those subjects who enroll <14 days after end of study visit or from Screening visit in A3921092 for those subjects who enroll into this study >14 days after end of study visit in qualifying study), will be recorded as adverse events and evaluated further, as clinically warranted.

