Appendix 4. Guidelines for Safety Monitoring, Dose Adjustments and Discontinuation

The following protocol-specified guidelines for safety monitoring and discontinuation are to be implemented.

For guidelines that reference changes from baseline, the baseline reference value is the baseline value from the qualifying study for all subjects who enter A3921092 within 2 weeks of the EOS visit of the qualifying study. For any subject who has >14 days between the EOS visit of the qualifying study and entry into A3921092, the baseline reference value is the value from the baseline visit of the A3921092 study.

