3. Cardiovascular (CV) Risk Factor Assessment includes multiple assessments such as smoking status, average weekly alcohol consumption, and family history of premature coronary heart disease (CHD) (See [Section 7.4](#) of LTE for complete list). This should be done as part of the Month 24 visit in study A3921092.
4. Complete physical exam should be performed annually (Baseline and Month 12 or Early Termination) and includes: height, weight, general appearance, skin, HEENT (head, eyes, ears, nose and throat), heart, lungs, abdomen, lower extremities, neurologic and lymph nodes. Targeted physical exam should be performed at other scheduled visits except Follow-Up and includes: weight, examination of heart, lungs, abdomen, lower extremities (for peripheral edema) and lymph nodes.
5. 12-lead ECG will be taken at sub-study baseline and Month 12 or Early Termination (ET) visit only. ECG will be evaluated by a central reader.
6. Tuberculosis annual screening procedures must be performed if not completed during the Month 24 LTE study visit in appropriate subjects. Annual TB screening will be conducted using Quantiferon-TB[®] Gold In-Tube test (QFT) for subjects in those countries in which TB incidence has been reported at a rate of >50 cases per 100,000 persons (see [Section 7.6.3](#)). All subjects with positive results (and who tested negative at their last QFT) must have chest radiograph performed and reviewed by a radiologist or pulmonologist as per local standard of care. Subjects who must have a PPD administered must return within 48-72 hours for evaluation.
7. Hematology includes: white blood cell (WBC) count/differential, hemoglobin, hematocrit, red blood cell (RBC) count and morphology, reticulocyte and platelet counts. Serum chemistry includes: urea nitrogen, creatinine, glucose, calcium, sodium, potassium, bicarbonate, chloride, total protein, total bilirubin, direct bilirubin, indirect bilirubin, alanine transaminase (ALT), aspartate transaminase (AST), alkaline phosphatase, gamma-glutamyl transferase (GGT), albumin and creatine kinase (CK). All hematology, clinical chemistry tests and HbA1C will be performed by the central laboratory; C-reactive Protein (CRP) will also be measured by central laboratory (results will be blinded).

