
- Cardiovascular Risk Assessment: smoking status, average weekly alcohol consumption and family history of premature coronary heart disease (see [Section 7.4](#) of LTE study).
- Physical Examination: Complete physical examination (height, weight, general appearance) skin (presence of rash), HEENT (head, eyes, ears, nose and throat), lungs (auscultation), heart (auscultation for presence of murmurs, gallops, rubs), extremity exam (presence of peripheral edema), abdomen (palpation and auscultation), neurologic (mental status, station, gait, reflexes, motor and sensory function, coordination) and lymph nodes.
- Waist and hips circumference.
- Blood testing: Central laboratory testing of Lipid Profile (fasting).
- Yearly TB testing if applicable.
- 12-lead electrocardiogram.
- Monitoring of adverse events and concomitant treatments. Record any modifications, deletions or additions.

- Drug dispensing.
- Observe subject taking the study drugs (tofacitinib and MTX or placebo) and record the dosing in the dosing log CRF.

6.1.3. Combined A3921092 & Sub-Study Switch/Baseline Visit at Month 30

For subjects with the Combined A3921092 Sub-study Switch/Baseline visit conducted at the scheduled A3921092 study visit of Month 30, the subjects must complete activities as indicated from M30 visit of A3921092 in addition to the following procedures at the combined screening/baseline visit.

- Informed consent obtained;
- Collect tofacitinib LTE investigational product supplies and complete accountability for the last visit of the main LTE study.
- Register for subject identification number.
- Randomization completed.

The following additional procedures will also be performed:

- Physical Examination: Complete physical examination (height, weight, general appearance) skin (presence of rash), HEENT (head, eyes, ears, nose and throat), lungs (auscultation), heart (auscultation for presence of murmurs, gallops, rubs), extremity exam (presence of peripheral edema), abdomen (palpation and auscultation), neurologic (mental status, station, gait, reflexes, motor and sensory function, coordination) and lymph nodes.
- 12-lead electrocardiogram.
- Yearly TB testing if applicable.
- Monitoring of adverse events and concomitant treatments. Record any modifications, deletions or additions.
- Drug dispensing.
- Observe subject taking the study drugs (tofacitinib and MTX or placebo) and record the dosing in the dosing log CRF.

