8.2. Statistical Analyses

Tofacitinib dose may be increased to 10 mg BID at study visits based upon investigator's discretion. Also, tofacitinib dose may be decreased (ie, 10 mg BID to 5 mg BID) for safety

reasons at any time. Hence changes in the dose are treatment related. Consequently, descriptive statistics will be displayed for just one treatment group: the entire cohort of subjects in which tofacitinib is dosed flexibly between 5 mg and 10 mg BID.

The baseline values for the safety endpoints come from the baseline of the qualifying study for patients who enroll within 14 days of the last visit of the qualifying study. For the patients whose enrollment are out of 14-day window, their baseline values of the safety endpoints will be from the baseline visit of this study, A3921092. The baseline values for all the efficacy or health-outcome endpoints come from the baseline of the qualifying study. In addition, as a sensitivity analysis for the ACR response rates and Δ HAQ-DI, the baseline value will be the baseline visit for A3921092 for patients whose enrollment is out of 14-day window.

All analyses will use FAS (Section 5.1) or FAS with some subjects excluded from analyses for certain endpoints (Section 5.4.1) except where indicated otherwise.

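### SAP 8.2 takes late enrollers' ECG baseline from a visit with no scheduled ECG, so as written it gives them no ECG change from baseline

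*SAP*

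**What the plan says.** The SAP sets the safety baseline by time of entry. Subjects enrolling within 14 days of their last qualifying-study visit use the qualifying-study baseline. For the rest, SAP 8.2 states that "their baseline values of the safety endpoints will be from the baseline visit of this study, A3921092". SAP Appendix 1 repeats this and lists Screening as a separate label, before the baseline visit. Neither place treats ECG differently from laboratory tests or vital signs.

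The protocol has two rules for these late enrollers. For the safety-monitoring guidelines, Protocol Appendix 4 says "the baseline reference value is the value from the baseline visit of the A3921092 study". For ECG, Protocol 7.6.2 takes the baseline "from Screening visit in A3921092 for those subjects who enroll into this study >14 days after end of study visit" in the qualifying study.

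Screening and Baseline are different visits for this group. Protocol 6.1.1.2 says of the Baseline visit: "This visit must occur 2-28 days after screening visit".

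Change from baseline in ECG measurements is an Other endpoint in SAP 6.3. SAP 8.2.3 plans a by-visit descriptive summary of it, following the Pfizer Data Standards (PDS) and using cumulative data from the main extension and the sub-study.

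**The concern.** The SAP carries over the protocol's general safety baseline and omits its ECG-specific one. The visit that the general rule points to has no scheduled ECG. A programmer who follows the SAP exactly would find the ECG baseline missing for every late enroller, and those subjects would drop out of the ECG change summary. Yet each of them has a pre-dose ECG, and Protocol 4.1.2, criterion 4, makes it an entry condition: "Screening 12-lead electrocardiogram (ECG) that does not demonstrate clinically relevant abnormalities (as determined by central reader").

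What is at stake is the completeness of one descriptive safety table. The following do not depend on this rule:

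- ECG abnormality counts that need no baseline
- adverse-event recording under Protocol 7.6.2
- laboratory, vital-sign and physical-examination data
- the sub-study's own ECG analysis, which has its own baseline

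**Working it through.** The plan gives no figure to reproduce. The check sets the baseline rule against the ECG schedule and then counts the ECGs affected.

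**Step 1: pre-dose ECGs scheduled for a late enroller**

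| Source | Screening | Baseline visit |
|---|---|---|
| Protocol Table 1, ECG row | marked | blank |
| Protocol 6.1.1.1 and 6.1.1.2 | ECG listed | no ECG listed |
| Protocol 7.6.2 | named as the baseline ECG | not named |
| SAP 8.2 and Appendix 1 | not used | named as the safety baseline |

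The scheduled count is 1 at Screening and 0 at the Baseline visit. Footnote 9 to Table 1 ("12-lead ECG will be taken at annual visits (Month 12, 24 and 36) and Early Termination (ET) visit only") adds no ECG at Baseline.

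**Step 2: what the SAP does when the baseline is missing**

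SAP 8.1.1 summarizes change only for endpoints measured at baseline, and SAP Section 7 does not impute missing endpoint values. With no baseline ECG, no change value can be formed. The wording in SAP 6.3 that allows a baseline in this or the prior study does not help, because SAP 8.2 then assigns late enrollers to the A3921092 Baseline visit. A rule taking the latest pre-dose value is written for the sub-study (SAP Appendix 6, Section 5) but not for the main extension.

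**Step 3: on-treatment ECGs scheduled for one late enroller**

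The main-extension ECGs follow footnote 9. For the sub-study, Protocol Appendix 10 says "12-lead ECG will be taken at sub-study baseline and Month 12 or Early Termination (ET) visit only". At a Month 24 or Month 36 switch, the annual-visit ECG and the switch ECG are the same recording. At Months 27, 30 and 33, Appendix 10 sections 6.1.2 and 6.1.3 add a "12-lead electrocardiogram" to the visit.

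| Course of subject | Scheduled on-treatment ECGs | Count | Change values, SAP rule | Change values, Screening baseline |
|---|---|---|---|---|
| Extension only, completes | M12, M24, M36 | 3 | 0 | 3 |
| Switch at M24, completes sub-study | M12, M24, sub-study M12 | 3 | 0 | 3 |
| Switch at M27, M30 or M33, completes | M12, M24, switch, sub-study M12 | 4 | 0 | 4 |
| Switch at M36, completes | M12, M24, M36, sub-study M12 | 4 | 0 | 4 |
| Early termination (ET) before M12 | ET | 1 | 0 | 1 |
| ET between M12 and M24 | M12, ET | 2 | 0 | 2 |
| ET between M24 and M36 | M12, M24, ET | 3 | 0 | 3 |

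If a subject terminates early from the sub-study, that ECG takes the place of the sub-study Month 12 ECG and the count is unchanged.

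**The case against.** The schedule itself is not in dispute. The strongest argument concerns consequence. SAP 8.2.3 defers the ECG summaries to the PDS, which were not supplied. If they define baseline as the last pre-dose value, nothing would be lost in practice. That stands as a possible mitigation, but the SAP states an explicit and different rule, and correct output should not depend on a programmer overriding it.

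A second argument is that Protocol 7.6.2 is an instruction for recording adverse events, so it does not define an analysis baseline and could be read as filling in the general SAP rule. The context is as described, but 7.6.2 is the protocol's only statement of which ECG is baseline. Even if it is set aside, the SAP still points to a visit without a scheduled ECG. A related argument is that the protocol uses the word baseline loosely: for late enrollers the complete physical examination in 7.6.4 is also done before dosing only at Screening. But SAP Appendix 1 labels Screening and Baseline separately, which leaves little room for a loose reading.

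Third, the counts are of scheduled ECGs, not entries in the by-visit table. SAP Appendix 1 keeps one observation per window, so an early-termination ECG on or before Day 379 would displace a Month 12 ECG in the same window (Days 296 to 379). This is correct, and the counts should not be read as table entries. It does not alter the zeros.

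Finally, a last-pre-dose rule is not identical to the Screening ECG named in 7.6.2. The two differ only if an unscheduled ECG is taken between Screening and the first dose.

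**Conclusion.** The concern holds. For subjects enrolled outside the 14-day window, the SAP's stated safety baseline yields no ECG baseline and conflicts with Protocol 7.6.2. Per subject the loss is every change value: 3 for an extension completer, 3 or 4 for a sub-study completer, and 1 to 3 for someone who leaves the extension early.

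This rests on three assumptions: the SAP is applied as written, no unscheduled ECG is taken at the Baseline visit, and the PDS do not override the rule. The number of late enrollers is not stated, so the share of the summary affected cannot be given.

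The importance is low. The endpoint is descriptive and classed as Other, and no primary or secondary endpoint is touched.

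**What to change.** Add one ECG-only sentence to SAP 8.2 and to the Baseline row of SAP Appendix 1: for subjects enrolled outside the 14-day window, the ECG baseline is the last A3921092 ECG before the first A3921092 dose, which is scheduled at the Screening visit in line with Protocol 7.6.2. Leave the Baseline-visit rule as it is for laboratory tests and vital signs.

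The cost is one sentence in two places, with no new data. These subjects' ECG baseline would normally be 2 to 28 days older than their laboratory and vital-sign baseline, a gap that the protocol already accepts by naming the Screening ECG.

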8.2.1. Analysis of Primary Endpoints

Safety analysis will include cumulative data from both the main LTE study and sub-study.

- Adverse events will be summarized according to Pfizer Data Standards (PDS).
- Incidence rate (IR) defined as the number of subjects with an event in the numerator divided by the study drug exposure in the denominator (expressed as the number of subjects with an event per 100 patient-years) will be calculated for deaths, SAEs, AEs leading to discontinuation and AEs of special interest. AEs of special interest include but may not be limited in the events listed in **Table 2** AEs of Special Interest. The event will be counted from subject's first dose to subject's last dose of study drug + 28 days. The denominator is the sum of the time to event or to subject's last dose of study drug + 28 days, whichever is earlier.

Table 2 AEs of Special Interest

Serious infections (SIs)
Herpes zoster (HZ)
Adjudicated opportunistic infections (OIs) excluding tuberculosis (TB) ^a
Hematologic events (anaemia, neutropenia, lymphopenia, and thrombocytopenia)
Adjudicated malignancies ^a
Adjudicated major adverse cardiovascular events (MACE) ^{a,b}
Adjudicated drug-induced liver injury (DILI) ^a and other hepatic events ^c
Renal events ^d
Adjudicated gastrointestinal (GI) perforations ^a
Adjudicated interstitial lung disease (ILD) ^e

Abbreviations: DILI = drug-induced liver injury; GI = gastrointestinal; HZ = herpes zoster; ILD = interstitial lung disease; MACE = major adverse cardiovascular events; MedDRA = Medical Dictionary for Regulatory Activities; OI = opportunistic infection; SI = serious infection; SMQ = Standardised MedDRA Queries; TB = tuberculosis.

a. Adjudicated by Adjudication Committees independent and external to Pfizer.

b. Components: cardiovascular death, non-fatal myocardial infarction, and non-fatal stroke.

c. Including SMQs: Hepatic failure, fibrosis, and cirrhosis, and other liver damage-related conditions; and Hepatitis, non-infectious.

d. Including Acute renal failure SMQ.

e. Adjudicated by an internal review committee.

- Safety laboratory tests will be summarized according to the PDS.
- The summaries for laboratory tests include contingency tables (eg, normal, high, low), and descriptive statistics for change from baseline by treatment group and visit. For the FACS, the endpoints to be summarized, which are subsets of lymphocytes and are measured at baseline, and every 3 months beginning at Month 3 visit, are as follows: $CD3^+$ (% , abs), $CD3^+CD4^+$ (% , abs), $CD3^+CD8^+$ (% , abs), $CD19^+$ (% , abs), $CD16^+/CD56^+$ (% , abs). Raw values as well as percent change from baseline will be summarized with descriptive statistics by visit.

